Ketamine regimen justification: In the Mount Sinai study, some PTSD responders maintained the therapeutic benefits from ketamine relative to midazolam for two weeks. However, symptom severity gradually increased between days 3-7 after ketamine.²⁷ This suggested that repeated infusions might provide sustained clinical benefit, consistent with other repeated dose studies.^{21,55} In addition, depression studies have demonstrated the following: 1) The efficacy of twice per week ketamine infusions are comparable to three times per week, 2) 0.2 mg/kg ketamine may possess antidepressant properties with a lower side effects profile, 3) Ketamine is efficacious in patients on stable antidepressant doses, and 4) There is an incremental benefit with repeated ketamine administration and a prolonged duration of treatment response.^{21,56-62} Therefore, we have selected a treatment regimen that is predicted to sustain the response observed following single infusion,²⁷ while testing the dose-related efficacy and longer-term safety of repeated dose ketamine in PTSD. Finally, although a current NIMH-funded trial will investigate the dose-response effect of a single dose ketamine on depressive symptoms in MDD (NCT01920555; Yale is an enrollment site, PI – [name]), the results from the depression study will not be sufficient to determine the dose response effects of repeated ketamine in PTSD. Our proposed study will provide critical information about the safety and efficacy of various ketamine doses, which will inform the implementation of ketamine in service-connected PTSD and may provide guidance to the development of novel safe NMDA receptor antagonists.

Blood Collection: We will collect blood samples at visits 2 (baseline; prior to first infusion), 3 (24-hour follow-up #1), 7 (prior to infusion #5), 11 (24-hour follow-up #2), 16 (24-hour follow-up #7). Four tube types at each proposed collection: 1) PAXgene DNA, 2) PAXgene RNA, 3) EDTA plasma tube, and 4) serum separator tube (SST). Standard operating procedures will be followed for blood processing, storage, and shipping.

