primary hypotheses with at least 80% power at two-sided alpha level of 0.05. In particular, with 53 subjects per group we have 87% power to detect a treatment by time interaction of magnitude $f=0.24$ and 80% power to detect pairwise differences of magnitude $d=0.6$ or higher at two-sided alpha level of 0.05. Holm-Bonferroni adjustment will be used for the pairwise comparisons and is taken into account in the power calculation so that the family-wise error rate for the pairwise comparisons is kept at 0.05 level. Testing of between group differences over time will be performed within the mixed effects models which are expected to be even more powerful since they use all available data on each individual including data on subjects who dropout or have intermittent missing data due to non-compliance with the treatment schedule. To address potential limitations related to the external validity, we have expanded the age range (18-70), included active duty military personnel and non-OEF/OIF/OND Veterans, and will use stratified randomization to match and balance on study site and alcohol use comorbidity during the trial. Additionally, we plan to track participant duty status, years since trauma and treatment history, and examine these factors in post-hoc analyses.

Analysis plan: Descriptive statistics will be calculated prior to statistical analysis. Distributions of quantitative variables will be assessed for normality using normal probability plots and Kolmogorov-Smirnov statistics and transformations or non-parametric methods will be used as necessary. All statistical tests will be two-sided. Uncorrected alpha level of 0.05 will be used for testing the primary hypothesis as described below. Pairwise post-hoc comparisons and tests of secondary outcome measures will be adjusted using Holm-Bonferroni procedure. Randomized treatment groups will be compared at baseline on potentially confounding factors (e.g. age, sex, history of substance abuse) and variables that are significantly different between groups will be included as additional covariates in the models below. All analyses will be intent-to-treat.

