Exploratory aim 1: Safety of repeated ketamine exposure. 1) Changes in psychotic (PANSS), dissociative (CADSS) and cognitive symptoms (Cogstate) across time between groups will be assessed using mixed effects regression models with group as between-subject factor and time as a within-subject factor as described in the primary specific aim. We anticipate significant differences between ketamine and placebo during infusions but no significant between-group differences at discharge and at the two-week and one month follow-up. 2) Descriptive statistics will be calculated for consumption of recreational substances prior to randomization, throughout the trial and for 4 weeks following the last ketamine exposure. If sufficient sample size is available for analytic modeling of recreational substance use between groups, mixed effects models or nonparametric regression will be used to test for differences between groups. 3) Breath alcohol levels over time will be compared as described for Aim 1. 4) Descriptive statistics will be calculated to summarize types and rates of adverse events between groups. Rates of adverse events will be compared using Fisher's exact tests since numbers of adverse events per arm may be small. Exact logistic regression analyses will be used to assess effects of additional potentially confounding covariates on adverse events if possible (i.e. if sufficient numbers of adverse events are present in the sample to allow for such analysis).

Exploratory aim 2: To assess the durability of ketamine effects on PCL-5, we will use mixed effects regression models in the subjects who responded to the study drug by the end of the double-blind treatment. Week post-treatment will be a within-subject factor and the treatment group a between-subject factor in this analysis, and we will covary for severity at the end of treatment. We will perform pairwise comparisons over time to determine if subjects maintain improvements on ketamine during the 4-week follow-up.

Exploratory aim 3: To test the clinical significance of PCL-5 changes, we will perform secondary mixed model analyses on CAPS-5, CGI, VR-12, PROMIS, WHYMPI, and Pain-NRS, using the same approach as described in Aim 1.

Exploratory aim 4: To test the integrity of the blind, we will use chi-square tests and ANOVA models to compare the accuracy and level of confidence in the guessed treatment assignment between groups.

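### Durability (Exploratory aim 2) rests on pairwise difference tests with no stated reference time, confidence interval or margin, and such tests cannot show that benefit is maintained

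*Protocol*

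**What the plan says.** Durability among responders is the fourth of the four questions that the protocol sets at its start. It appears as item 2 of the secondary specific aims and as Exploratory aim 2 in the analysis plan.

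- **Population:** the model is fitted "in the subjects who responded to the study drug by the end of the double-blind treatment".
- **Model:** on the covariate, the plan says "we will covary for severity at the end of treatment"; on the factors, it says "Week post-treatment will be a within-subject factor and the treatment group a between-subject factor in this analysis".
- **Test:** "We will perform pairwise comparisons over time to determine if subjects maintain improvements on ketamine during the 4-week follow-up".
- **General rules (Analysis plan):** on sidedness, "All statistical tests will be two-sided"; on multiplicity, "Pairwise post-hoc comparisons and tests of secondary outcome measures will be adjusted using Holm-Bonferroni procedure".
- **Visits:** the protocol text lists Days 25, 28, 35, 42, 49 and 56 as follow-up after infusion 8. Table 2 has PCL-5 at all of them, calls Day 25 the second follow-up, and marks Day 28 as an optional open-label visit.
- **SAP:** the follow-up PCL-5 and CAPS-5 data go into mixed models that covary for pretreatment severity and exclude people who had open-label treatment. It names no follow-up contrast, reference time or criterion for maintained benefit. Its focused contrasts run from baseline to 24 hours after the first and after the last infusion.

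**The concern.** The question is whether the improvement present at the end of treatment is kept. Two things stand between the stated method and an answer.

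First, a two-sided test of difference can support a statement of maintenance only by failing to reject, and failing to reject is also what a small or noisy sample produces. Holm adjustment makes it more likely. No interval or margin bounds the loss that would still count as maintained.

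Second, the reference is not named. End-of-treatment severity is a covariate, and the time factor holds post-treatment weeks, so the natural reading is that follow-up weeks are compared with one another. Those contrasts cannot see a loss that is complete before the first of them. Such a loss is plausible. The regimen justification reports that, in the earlier single-infusion PTSD study, "symptom severity gradually increased between days 3-7 after ketamine". Infusion 8 is on Day 24, and the first visit after Day 25 that is not optional in Table 2 is Day 35, which is 35 − 24 = 11 days later. The same section also says that some responders kept their benefit for two weeks, so early loss is possible but not certain.

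At stake is a report of durable benefit that the analysis did not establish.

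**Working it through.** **1. The plan's only pairwise power figure.** The sample size section gives 80% power for d = 0.6 with 53 per group under Holm-Bonferroni, so that "the family-wise error rate for the pairwise comparisons is kept at 0.05 level". At the second Holm step (alpha 0.025), power = Φ(0.6·√(53/2) − 2.241) = Φ(3.089 − 2.241) = Φ(0.847) = 0.80. Simulating Holm over three arms with true means 0, 0.2 and 0.8 also gives 0.80 for high versus low dose. The figure reproduces, but it concerns the randomised groups. None is given for durability.

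**2. Literal reading: six pairs among Days 35, 42, 49 and 56.** Suppose a loss L is complete by Day 35 and the scores are flat afterwards. Every week then has mean μ + L, and each pair has expected difference (μ + L) − (μ + L) = 0. L cancels. So does the end-of-treatment covariate, if it has one slope for all weeks. All six null hypotheses are true, and the chance of no significant pair is 1 minus the family-wise error rate, which is at least 95% under Holm.

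**3. Simulation.** Paired t tests stand in for the mixed-model contrasts, with Holm at 0.05 within one arm and 8,000 to 20,000 runs per case. Assumed, because the documents give none of these: 15, 25 or 35 responders, the size of the loss in SDs of PCL-5, and the within-person correlation. The correlation is compound-symmetric or serial, at 0.5 and 0.8 for the first row. For the Day 25 rows it is compound-symmetric 0.5 or serial 0.7.

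Chance of no significant pair:

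| Pairs tested | Loss, complete by Day 35 then flat | n = 15 | n = 25 | n = 35 |
|---|---|---|---|---|
| Four weeks, 6 pairs | any size | 96% | 96% | 96% |
| Day 25 added, 10 pairs | 0.5 SD | 64-65% | 35-39% | 16-19% |
| Day 25 added, 10 pairs | 0.8 SD | 19-22% | about 2% | 0.1-0.2% |
| Day 25 added, 10 pairs | 1.0 SD | 4-6% | under 0.1% | 0% |

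The unrounded range for the first row is 95.7-96.1%.

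**4. How far the 96% depends on its assumptions.** These cases keep the four weekly visits and no Day 25 level:
- without Holm: 79-81%;
- Holm over 18 tests in three arms: 95.3%;
- 75% of a 0.8 SD benefit lost by Day 35 and the rest by Day 56: 90% (n = 25) and 88% (n = 35);
- a 0.8 SD benefit lost in a straight line from Day 35 to Day 56: 9% (n = 25).

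The blind spot is therefore specific to early loss. A steady loss across the follow-up weeks is often seen.

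**5. What an interval would give.** The half-width of a 95% CI for a mean change is about t·√(2(1 − ρ)/n) in SD units. With n = 25 and t = 2.064, this is 2.064·√(1/25) = 0.41 SD at ρ = 0.5 and 2.064·√(0.4/25) = 0.26 SD at ρ = 0.8.

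**The case against.** A reader might infer that this trial would call a wholly lost benefit maintained 96% of the time. The documents do not support that. No section says that a non-significant result will be called maintenance. The reference time is unstated, not fixed at the follow-up weeks. Day 25 is listed as a follow-up visit for everyone, and making it a level changes the result sharply. The sample size section uses the word pairwise for comparisons between treatment groups, and that reading is not excluded here either. The 96% is 1 minus the family-wise error rate under one reading and one pattern of loss. It is not a measured property of this trial.

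Other outputs could also reveal a loss. The secondary aim promises qualitative and quantitative characterisation. CAPS-5 is taken at Days 25 and 56. In the protocol's model, the adjusted week mean minus the mean end-of-treatment score already estimates the loss. The aim is exploratory, and the go decision rests on the primary analysis.

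Day 25 is also an imperfect reference, because responders are selected on their end-of-treatment score. One simulation assumed a PCL-5 SD of 12, 53 per arm, response as a 25% PCL-5 drop and no true change after Day 25. It gave an apparent rise of 2.1 to 4.3 points, and Day 56 versus Day 25 was significant in 32-60% of runs. These figures move with the assumed mean drop and correlation.

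All of this limits the size of the point. It does not supply the missing contrast or interval. Comparing groups at each week asks whether the arms differ, not whether improvement is kept. The primary aim, by contrast, names its contrast (baseline to end-point) and promises effect sizes with confidence intervals.

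**Conclusion.** The point holds as a fault in the kind of test. Difference tests with no reference time, interval or margin cannot establish maintenance under any reading of the sentence.

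The size depends on the reading. With pairs among Days 35 to 56 only, Holm within arm, and a loss complete by Day 35 and then flat, about 96% of analyses show no significant pair, whatever the loss. With Day 25 as a level and an assumed 25 responders, a 0.5 SD loss is missed 35-39% of the time and a 0.8 SD loss about 2%. The documents do not settle which reading applies, and they give neither the number of responders nor the size of loss to expect.

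Severity is minor to moderate. Durability is one of the trial's four questions, but the aim is labelled exploratory and does not touch the primary test.

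**What to change.** Replace the sentence on pairwise comparisons in Exploratory aim 2, and add the same text to the SAP:

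> *For each arm we will estimate, from the mixed model, the mean PCL-5 change from Day 25 and from Day 0 to each follow-up week (Days 35, 42, 49, 56) with 95% CIs. Durability will be judged from these estimates and CIs, and a non-significant difference will not be taken as evidence of maintenance.*

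Three additions belong with it:

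- **Selection.** State that responders are chosen on their end-of-treatment score, so regression to the mean inflates the apparent loss from Day 25.
- **Covariate.** Reconcile the protocol (end-of-treatment severity) with the SAP (pretreatment severity). If the Day 25 PCL-5 becomes an outcome row, it should not also be the covariate. Taking change from Day 25 as the outcome avoids this.
- **Margin.** Whether to set a retention margin, and where, is for the sponsor. The SAP is written in the past tense and reports results, so a margin set after the data were analysed must be labelled post hoc. The estimates and intervals do not need one.

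The cost is a few sentences. PCL-5 is already scheduled at every visit involved. The downside is wide intervals in the responder subset (roughly ±0.26 to ±0.41 SD at 25 responders, as worked above), so maintenance will be claimed less often.

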3. Clinical significance of PCL changes: Following the lead of the VA Cooperative studies, we will use the PCL-5 as the primary outcome variable due to its sensitivity to pharmacotherapy effects, lower respondent burden, and to reduced site-specific rater effects relative to the Clinician-Administered PTSD Scale (CAPS). The CAPS-5 (using the DSM-5 criteria for the diagnosis of PTSD) will be obtained at baseline, at the end of randomized treatment, and at 4-week follow-up. Global/functional impact of treatment will be evaluated with the Clinical Global Impression Scale (CGI), and the Veterans Rand 12-item Health Survey (VR-12).

4. Integrity of the blind: At the end of the randomized treatment, participants will be asked to name the study arm that they believe they were assigned to and to identify their level of confidence in their designation.

II. BACKGROUND

There is a tremendous need to test novel pharmacotherapeutic approaches to PTSD. PTSD is a leading cause of disability amongst trauma-exposed military and civilians alike. The National Comorbidity Survey Replication (NCS-R) estimates the lifetime prevalence of PTSD among adult Americans to be 6.8%.⁹ The US Department of Veteran Affairs estimates that PTSD afflicts 11% of Veterans of the war in Afghanistan and 20% of Iraqi war Veterans. While antidepressant medications are currently available, the efficacy of these medications is limited.¹⁰⁻¹² Currently, only two medications, both selective serotonin reuptake inhibitors (SSRIs), have FDA approval for the treatment of PTSD. These medications take weeks to months to reach full clinical effects. In civilian treatment seeking populations, fewer than half of the patients achieve full remission

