1. Alcohol Use Disorders Identification Test (AUDIT): The AUDIT was developed by the World Health Organization as a brief, 8-item measure that assesses alcohol use over the past year, specifically screening for excessive drinking and some specific consequences of harmful drinking.
2. Assessment of Rapid Affect Changes (ARAC): The ARAC is a 31-item self-report measure assessing affective symptoms (e.g., sadness, guilt, anxious, discouraged, etc.) on a 5 point scale for how the participating is “feeling including right now,” where 0 indicates “not at all,” 1 indicates “a little bit,” 2 indicates “moderately,” 3 indicates “quite a bit,” and 4 indicates “extremely.”
3. Blinding Form – This is a brief form that asks participants their thoughts regarding which treatment arm they were randomized into. This gives us information regarding how successful the research design and research staff were at maintaining the blind.
4. Brief Inventory of Psychosocial Functioning (B-IPF): The B-IPF is a 7-item self-report measure assessing the respondents’ level of functioning across seven domains: romantic relationships, relationships with children, family relationships, friendships and socializing, work, training and education, and activities of daily living. Respondents rate the degree to which they had trouble in these domains across the last 30 days.
5. Clinical Global Impressions (CGI) and Patient Global Impressions (PGI): The CGI and PGI are widely used instruments, which assess overall severity of illness on a 1 to 7 point scale with 1 indicating “normal, not at all ill” and 7 indicating “among the most extremely ill patients.” These instruments also assess global improvement on a 1-to-7 point scale with 1 indicating “very much improved,” 4 indicating “no change” and 7 indicating “very much worse.”
6. Clinician-Administered Dissociative States Scale (CADSS): The CADSS contains self and interviewer-administered items including 5 subscales, generated a priori, evaluating dissociation including altered environmental perception, time perception, spatial/body perception, derealization and memory impairment.

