SAFTEE	X	X	X	X	X	X	X	X	X	X
VR-12	X		X			X		X	X	X
WHYMPI	X		X			X		X	X	X
Cogstate	X		X			X		X		X
Physical Exam	X									
Medical History	X									
Routine Lab Tests	X									
Breathalyzer	X	X (PRE INF)	X	X (PRE INF)	X (PRE INF)	X	X (PRE INF)	X	X	X
ECG	X									
Serum Pregnancy Test	X									
Urine Pregnancy Test		X (PRE INF)		X (PRE INF)	X (PRE INF)		X (PRE INF)			
Blood Collection/Banking (e.g., DNA, RNA, Plasma, Serum)		X	X		X	X				X
Vital Signs	X	X (PRE,10, 20, 40)	X	X (PRE,10, 20, 40)	X (PRE,10, 20, 40)	X	X (PRE,10, 20, 40)	X	X	X
Infusion		X		X	X					
Open-Label Infusion							X			
IE Blinding Form						X				
Blinding Form						X				

*No study procedures will be completed prior to completion of the Informed Consent. The "Day" number is an approximation and the actual day may vary depending on delays in prior visits.

Test Days

Screening

Informed consent, physical examination and health assessment, ECG, laboratory tests, concomitant medications, MINI psychiatric assessment, and demographic information.

- Measures including, but not limited to, the DVBIC Brief TBI Screen, CAPS-5, PCL-5, MADRS (item 10 only), QIDS-SR, ARAC, CGI, PHQ-9, GAD-7, AUDIT, ISI, PROMIS Sleep, WHYMPI, Pain-NRS, VR-12, Cogstate, QDS will be administered. Refer to Table 2 for the full battery of measures and administration intervals.
- No more than 200 mL of blood will be collected for routine laboratory tests.
- After completing the screening and being deemed eligible for participation in the study, subjects will be randomized.

Infusion session 1 (Day 0)

- Infusions will take place at Biostudies, nursing/medical coverage will be provided by [name] [name] group, and will follow all related hospital and Biostudies standard operating procedures and policies.
- Breath alcohol, and urine pregnancy test;
- Blood collection for the biomarkers banking.
- AE Assessment since last visit;
- Intravenous lines started; Vital signs;
- Measures including, but not limited to, the PCL-5, MADRS, QIDS-SR, ARAC, CGI, GAD-7, PHQ-9, QDS, ISI, and will be completed prior to the study drug administration (refer to Table 2).
- Study drug will be infused over 40 minutes.
- Vital signs will be recorded at approximately 10, 20, and 40 minutes during infusion unless closer monitoring is clinically indicated.
- ARAC, CADSS and PANSS will be completed at 30 and 120 min following the start of the study drug infusion.

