Statistical Consideration: Group assignment: Stratified randomization will be used to balance assignment by infusion center, comorbid alcohol use disorder and to decrease the chance of accidental unblinding. The randomization assignment scheme will be developed by the statistician of the study, [name], Co-Director of the CAP Data and Biostatistics Core in collaboration with the Core Director at UTHSCSA ([name]). Blinded dose codes will be sent to each of the site pharmacists who will prepare the infusions so as to maintain the double blinding. Both ketamine and saline are odorless and colorless and research staff and subjects will not be able to discern between the placebo and active medication. Ketamine will be stored in the pharmacy according to the procedures for controlled substances and any opened vials will be discarded according to hospital policy. The study drug will be prepared and dispensed by the research pharmacy. Both the rater and the participant will be asked whether they have deduced their treatment arm at the end of each participant's infusion treatments. Blinding will be maintained throughout the study. [name] and the CAP Data Management and Biostatistics Core will maintain the list of unblinded assignments for both sites and the research pharmacists will also each have a list of unblinded assignments for their site. Randomization codes will be kept in a secure and locked area within each research pharmacy, where only pharmacy personnel have access. In the case of medical emergency, the blind may be broken by site-designated study personnel by calling the research pharmacist and following standard procedure for caller identification and research study identification.

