a. ***Ketamine*** has been administered to over 10,000 patients and reported in greater than 100 individual research investigations, including many over the past three decades from our research group. Since 1989, we have administered ketamine on over 800 occasions to over 300 subjects. Our group pioneered ketamine studies in healthy subjects,⁶⁴⁻⁷¹ and in depression,^{6,72,73} and we have extensive experience in ensuring participants' safety.⁷⁴ Ketamine has a wide margin of safety and is typically provided in doses of 1-4.5 mg/kg IV over 1 minute as a sole anesthetic agent. In the majority of psychiatric investigations in depressed subjects to date, ketamine has been administered at subanesthetic doses (typically 0.5mg/kg) infused over 40 minutes. Based on extant literature using subanesthetic doses of ketamine in a medical setting, it has been demonstrated that the acute psychomimetic and temporary perceptual disturbances that may follow ketamine infusion and its potential to exacerbate trauma recall post-infusion, are transient in nature starting within minutes of ketamine infusion and lasting less than 2-hours post-infusion.⁷⁴ In considering the implications of these adverse effects, it is important to note the consistent evidence that these temporary symptoms are dose-dependent with increased prevalence of symptoms at higher doses of ketamine.^{68,75,76} Members of our research team have administered doses exceeding 0.5 mg/kg of ketamine to healthy subjects and have successfully managed the transient nature of side-effects at this lower-dose.^{64-67,77,78} The dosages of ketamine selected for this clinical trial (0.5 mg/kg and 0.2 mg/kg infused over 40 minutes) produces blood levels that are 1/20 to 1/5 of those produced clinically when ketamine is used as an anesthetic.

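### Exploratory aim 4 compares guess accuracy between arms, which does not test whether the guess depends on the assigned arm: it misses equal failure and over-rejects when guesses lean to one arm

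*Protocol*

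**What the plan says.** In the protocol's analysis plan, Exploratory aim 4 sets out a comparison by arm whose purpose is "to compare the accuracy and level of confidence in the guessed treatment assignment between groups", using chi-square for the first and ANOVA for the second. The quantity compared is therefore correct versus incorrect, by arm, alongside a confidence rating.

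The data needed for a fuller analysis are collected. Under the secondary specific aims, item 4 says: "participants will be asked to name the study arm that they believe they were assigned to and to identify their level of confidence". The description of the Blinding Form (measure 3) says that it "asks participants their thoughts regarding which treatment arm they were randomized into". The group-assignment paragraph under Statistical Consideration adds that "Both the rater and the participant will be asked whether they have deduced their treatment arm". In Table 2 the Blinding Form and a second form, the "IE Blinding Form", are marked at Visit 11 only, the day after the eighth infusion.

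Neither the protocol nor the SAP text supplied plans a cross-tabulation of guessed by assigned arm, a comparison of accuracy with chance, or a blinding index. The supplied SAP text describes no blinding analysis.

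**The concern.** A blind is intact when knowing a participant's arm tells you nothing about the guess. The planned test asks something else: whether the proportion correct differs between arms. The two questions come apart in both directions. If participants in all three arms identify their treatment equally well, the proportions agree and the test has nothing to detect. If nobody can tell but most people prefer to name one arm, that arm looks accurate, the others do not, and the test rejects.

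The primary outcome is self-rated (PCL-5) and the comparator is saline. The section on protecting subject safety says of the acute effects that "these temporary symptoms are dose-dependent with increased prevalence of symptoms at higher doses of ketamine", so partial unblinding is foreseeable. Readers will use the blinding result to judge how far a treatment difference might reflect expectation. A p-value that can be non-significant after failure and significant with the blind intact does not help them.

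**Working it through.** **Inputs.**
- Three arms, allocated 1:1:1 (Primary specific aim; Therapeutic Risks).
- About 53 completers per arm when guesses are taken, and about 66 randomized (Section IV.A, Subjects).
- Alpha 0.05. The protocol states this for the primary hypothesis and gives none for aim 4, so it is assumed here.
- Guess distribution: none in the documents. All patterns below are assumptions, shown over a range.

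Aim 4 states no power, rate or threshold, so there is no figure to reproduce.

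**Step 1: the two null hypotheses.** With an intact blind, P(guess j | arm i) = q_j for every arm i. Accuracy in arm i is then q_i. Accuracies are equal only if q = (1/3, 1/3, 1/3), but they always sum to 1 in expectation when every guess names an arm. Conversely, equal accuracy at any level other than 1/3 is incompatible with independence. This step needs no assumed distribution.

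**Step 2: the two statistics.** Let c_i be the number correct in arm i, n the number per arm and p the pooled proportion correct.
- Planned: X² = Σ(c_i − np)² / [np(1 − p)], 2 df.
- Independence: X² = ΣΣ(O − E)²/E over the 3 x 3 table, 4 df.

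**Step 3: three worked tables, 53 per arm.**
- *Equal failure*, 27 correct and 13/13 wrong in each arm. All c_i are equal, so the planned X² = 0 (p = 1). Every E = 53/3 = 17.67, so the 3 x 3 X² = 3 × [(27 − 17.67)² + 2(13 − 17.67)²]/17.67 = 22.2 (p = 0.00018). Sum of accuracies 81/53 = 1.53 (95% CI 1.30-1.76).
- *Ketamine recognised, dose guessed by coin-flip, placebo about 70% correct*, rows [37,8,8], [0,27,26], [0,26,27]. Here p = 91/159 = 0.572 and np = 30.33. Planned X² = (6.67² + 3.33² + 3.33²)/(53 × 0.572 × 0.428) = 5.14 (p = 0.077). The 3 x 3 X² = 96.5 (p < 0.0001). Sum 91/53 = 1.72 (1.49-1.94).
- *Intact blind with a preference*, 13/13/27 in every arm. Planned X² = [2(13 − 17.67)² + (27 − 17.67)²]/(53 × 2/9) = 11.1 (p = 0.0039). The 3 x 3 X² = 0 (p = 1). Sum 53/53 = 1.00 (0.79-1.21).

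**Step 4: rejection rates**, 20,000 simulated trials per pattern, 53 per arm.

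| Assumed pattern | Planned test | 3 x 3 test |
|---|---|---|
| Equal failure, 40 / 45 / 50 / 60-90% correct | 4.7-5.1% throughout | 25 / 69 / 95 / 100% |
| Intact, guesses even | 5% | 4.5-5.2% |
| Intact, 40/30/30 | 19% | 4.5-5.2% |
| Intact, 45/27.5/27.5 | 49% | 4.5-5.2% |
| Intact, 50/25/25 | 81% | 4.5-5.2% |
| Intact, 10/10/80 | 100% | 4.5-5.2% |
| Ketamine recognised, placebo 30 / 40 / 50 / 60 / 70 / 80 / 90% correct | 58 / 17 / 5 / 16 / 58 / 93 / >99% | 100% throughout |
| Unequal failure, 60/40/85% or 45/45/80% correct | 98-100% | 100% |

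Analytic check for 50/25/25: the noncentrality is λ = 53 × [(1/6)² + 2(1/12)²]/(2/9) = 9.94, which gives 81.3%, in line with the simulated 81%.

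At 66 per arm the planned test rejects 4.8-5.1% under equal failure, 23/59/89/100% under the four intact leans, and 69/20/5/20/69/98/>99% in the ketamine-recognised series.

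**Step 5: why not test each arm against 1/3.** Under the intact 50/25/25 split, an exact binomial test against 1/3 rejects 71% of the time in the favoured arm and 19% in each of the others. It reacts to preference in the same way.

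**The case against.** The sentence is a one-line summary. It speaks of chi-square tests in the plural and the form collects a named arm, so a guess-by-arm table may have been intended. The aim is labelled exploratory in the analysis plan, no decision depends on it, and the table could be built from the same data at reporting. Dose-dependent symptoms make unequal accuracy at least as plausible as equal accuracy, and there the planned test performs well. The plan also compares confidence, which the simulations do not cover. Finally, a non-significant 3 x 3 test does not establish an intact blind, and the form may allow a non-committal answer.

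Several of these points stand. The planned test does detect clearly unequal failure, and in the ketamine-recognised series it misses mainly when placebo accuracy is about 40-60%. The 3 x 3 test has only 25% power when every arm is 40% correct. The size of the problem depends on patterns the documents do not give. But the text names accuracy compared between groups. Even where that test rejects, its p-value does not say whether the blind failed or guesses leaned one way. The confidence comparison does not close the gap, because confidence can be equally high in every arm after the blind has failed.

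**Conclusion.** The concern holds. As written, the accuracy chi-square tests a null hypothesis that neither implies an intact blind nor follows from one. That result is algebraic. Its practical size rests on assumed guess patterns, 53 guesses per arm and alpha 0.05. Under those assumptions the test keeps its nominal 5% rejection rate however badly the blind has failed, provided it fails equally. With the blind intact, its false-positive rate rises from 19% under a mild lean to 81% or more once half the guesses name one arm. The primary efficacy analysis is untouched; what changes is how its result can be interpreted. This should be corrected before the blinding data are analysed.

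**What to change.** For participants, replace the accuracy-by-arm chi-square with a test of association between guessed and assigned arm in the 3 x 3 table. Add a column if the form allows a non-committal answer.

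- Report the full table with per-arm accuracies and 95% confidence intervals. Read the accuracies jointly: their expected sum is 1 under an intact blind when every guess names an arm. A sum near 1 does not by itself prove independence, and neither does a non-significant test.
- Do not test each arm separately against 1/3. A per-arm blinding index is optional, and confidence may still be compared descriptively.
- Apply the same table to raters only if their form records a named arm. The protocol says only that raters are asked whether they have deduced it.
- State that guesses are taken at Visit 11 only, after eight infusions, so a correct guess may reflect symptom change as well as perceived drug effects.

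For participants the cost is analysis wording, since the named arm and confidence are already collected. For raters the content of the form has to be checked first; no new data are requested.
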